3.1.1 Primary Aims

The primary aim of this study is to assess whether combined MUS and peri-operative BPTx is superior to MUS alone for improving MUI symptoms in women electing surgical treatment.

3.1.2 Secondary Aims

Secondary aims of this study include the following:

1. Assess whether combined MUS+BPTx is superior to MUS alone for improving change in OAB symptoms at 1 year in women electing surgical treatment.
2. Assess whether combined MUS+BPTx is superior to MUS alone for improving change in SUI symptoms at 1 year in women electing surgical treatment for MUI.

3.1.3 Exploratory Aims

Exploratory aims of this study include the following:

1. Assess whether combined MUS+BPTx is superior to MUS alone for improving the number of urgency and urge incontinence episodes on bladder diary at 1 year following MUS surgery.
2. Compare time-to-failure between MUS+BPTx versus MUS alone, where failure is defined as initiation of any additional treatment for lower urinary tract symptoms (SUI, UUI/OAB, or voiding dysfunction).
3. Develop models to identify predictors of change of MUI, OAB, and SUI outcomes measured using the UDI between baseline and 1 year post-treatment.
4. Compare quality of life outcomes, Patient Global Impression-Improvement (PGI-I), and Patient Global Impression-Severity (PGI-S) between groups
5. Describe rates of reoperation (sling revision) for worsening OAB symptoms after MUS and to compare the proportion of women in each group initiating additional treatment for SUI and/or OAB, and the types of additional treatment (BPTx, medications, other)
6. Determine MIDs and clinically meaningful definitions of MUI that predict clinical outcomes using cut-offs and combinations of standardized measures
7. Compare pelvic floor muscle strength changes between women randomized to combined MUS+BPTx versus MUS alone and to estimate associations between pelvic floor muscle strength improvement and UI symptoms. We will also explore predictors of unsuccessful pelvic floor muscle strengthening.
8. Determine the cost effectiveness of combined midurethral sling (MUS) and peri-operative behavioral/pelvic floor therapy (BPTx) compared to MUS alone for the treatment of MUI symptoms

3.2 Outcomes

3.2.1 Primary Outcomes

The primary outcome for this study is the mean change from baseline in UDI-total score at 1 year postoperative. The MID for the UDI-total score published by Dyer et al is estimated to be 35 points.⁵⁰

3.2.2 Secondary Outcomes

The secondary outcomes for this study are the mean change from baseline in the UDI-irritative and -stress subscales. The MID for the UDI-irritative score published by Dyer et al is estimated to be 15 points⁵⁰ and the MID for the UDI-stress score published by Barber et al is estimated to be 8 points⁵¹

3.2.3 Exploratory Outcomes

Exploratory outcomes for this study include time-to-failure (defined as initiation of any additional treatment for lower urinary tract symptoms such as SUI, UUI/OAB, or voiding dysfunction), change from baseline quality of life outcomes at 1 year postoperative, global impression scales (PGI-I, PGI-S), change from baseline number of urgency and urge incontinence episodes at 1 year following MUS surgery (as determined by a bladder diary), reoperation rates for worsening OAB symptoms after MUS and additional treatments for SUI and/or OAB (both rates and types), and change from baseline measures of pelvic floor muscle strength at 1 year post-operative (Peritron Perineometer readings).

[figure not shown]
3.2.4 Safety Outcomes

Safety outcomes will be assessed in a descriptive manner at each DSMB meeting without formal statistical tests. This will include the need for sling revision due to worsening OAB symptoms. There is no established stopping rule to guide what sling revision rate is “appropriate” for worsening OAB symptoms in this population.

4 STUDY METHODS

4.1 Overall Study Design and Plan

The study is a multi-center, randomized, surgical trial of women with MUI who have elected to undergo surgical treatment for SUI. Participants will be randomized to a peri-operative BPTx program + MUS surgery versus MUS surgery alone. The purpose is to compare combined MUS+BPTx versus MUS alone (control) on improving MUI symptoms at 1 year. A study schematic is shown below:

4.2 Study Population

4.2.1 Subject Characteristics

Inclusion and exclusion criteria for the ESTEEM trial are as follows:

Inclusion Criteria:

1. Presence of both SUI and UII on bladder diary; and > 2 IEs/3 days
 - a. 1 Stress IE/3 days
 - b. 1 Urge IE/3 days
2. Reporting at least “moderate bother” from UII item on UDI: “Do you usually experience urine leakage associated with a feeling of urgency, that is a strong sensation of needing to go to the bathroom?”
3. Reporting at least “moderate bother” from SUI item on UDI: “Do you usually experience urine leakage related to coughing, sneezing, or laughing”
4. Diagnosis of SUI defined by a positive cough stress test (CST) or UDE within the past 18 months
5. Desires surgical treatment for SUI symptoms
6. Urinary symptoms >3 months
7. Subjects understand that BPTx is a treatment option for MUI outside of ESTEEM study protocol
8. Urodynamics within past 18 months

Exclusion Criteria:

1. Anterior or apical compartment prolapse at or beyond the hymen (>0 on POPQ), regardless if patient is symptomatic
 - a. Women with anterior or apical prolapse above the hymen (<0) who do not report vaginal bulge symptoms will be eligible
2. Planned concomitant surgery for anterior vaginal wall or apical prolapse > 0
 - a. Women undergoing only rectocele repair or another repair unrelated to anterior or apical compartment (i.e.: anal sphincter repair) are eligible
3. Women undergoing hysterectomy for any indication will be excluded
4. Active pelvic organ malignancy
5. Age <21 years
6. Pregnant or plans for future pregnancy in next 12 months, or within 12 months post-partum
7. Post-void residual >150 cc on 2 occasions within the past 6 months, or current catheter use
8. Participation in other trial that may influence results of this study
9. Unevaluated hematuria
10. Prior sling, synthetic mesh for prolapse, implanted nerve stimulator for incontinence
11. Spinal cord injury or advanced/severe neurologic conditions including Multiple Sclerosis and Parkinson’s
12. Women on overactive bladder medication/therapy will be eligible after 3-week wash-out period
13. Non-ambulatory
14. History of serious adverse reaction to synthetic mesh
15. Not able to complete study assessments per clinician judgment, or not available for 12-month follow-up

16. Women who only report “other IE” on bladder diary, and do not report at minimum 1 stress and 1 urge IE/3 days
17. Diagnosis of and/or history of bladder pain or chronic pelvic pain
18. Women who had intravesical Botox injection within the past 12 months
19. Women who have undergone anterior or apical pelvic organ prolapse repair within the past 6 months

4.3 Study Arm Assignment and Randomization

Once patients are enrolled, surgery should be scheduled within 3 months from enrollment, and randomization should occur within 4-6 weeks prior to the booked surgical date. The participant will be randomized to one of the two treatment arms (MUS or MUS+BPTx) using a web-based randomization system. The system will supply the site coordinator with a randomization code.

Randomization (1:1 to the two treatment arms) will be performed using permuted blocks, with a block size that is known only to the DCC and will be stratified by site and severity of baseline UUI (with a cut-off of ≥ 4 urge incontinence episodes on 3-day diary).

4.4 Masking and Data Lock

4.4.1 General Masking Procedures

Study surgeons and outcome assessors will be masked to treatment assignment. All outcome measures will be collected by masked outcome assessors. Study coordinators / clinical staff performing objective measurement of PFM strength will be masked (Aim 7). All patient-reported outcomes (PROs) will be administered prior to other clinical assessments or procedures.

It is not feasible to mask the patients or interventionists to the BPTx intervention due to the nature of the treatment being studied.

Study individual	Masking
Study participant	No
Interventionist	No
Outcome assessors (includes clinical staff performing PFM measurement)	Yes
Study surgeon	Yes

Efforts will be made by unmasked research assistant/staff members to remind the patient that the surgeon is masked to her treatment assignment. If she desires additional treatment, it is likely the surgeon would offer BPTx as additional treatment and she will be reminded that she can decline additional BPTx without revealing to her surgeon that she received the BPTx intervention. Such methods have been effective for past PFDN trials (e.g. OPTIMAL trial⁴²).

4.5 Database Lock

Database lock will occur when data collection has been completed prior to the final data analysis. Until it is agreed upon by the Steering Committee and the DCC that unmasking is not a risk to the study, only the DCC statistician(s) and data manager(s) working directly with the data will be

NetworkProtocol ESTEEM Statistical Analysis Plan

unmasked to the treatment assignments of individual study participants. Thus, data collection of longer-term outcomes will not be compromised by unmasking.

Network

Protocol ESTEEM Statistical Analysis Plan

4.6 Study Flow Chart of Assessments and Evaluations

	Baseline	Random-ization visit (T0 -5 wks)	2 wk preop (range 1-4 wks preop)	Surg MUS (T0)	Call (3-5d post-op)	2 wk post-Clinic	4 & 6 wks post	8 wk post-	3 mo post-Clinic and QoL	6 mo post-Clinic and QoL	12 mo post-Clinic and QoL
Window of time		± 7d	7-28d preop			± 7d	± 7d for each visit	± 7d	± 30d	± 30d	± 60d
Estimated duration of clinic and/or BPTx visit for each group		Both: 1.5-2hr	Control: N/A		Contr: N/A	Control: 1.5hr	Control: N/A	Control: 1hr	Both: 1.5hr	Control: 1.5hr	Both: 1.5-2hr
			Interv: 1.5hr		Interv: 15 min	Interv: 2.5hr	Interv: 1hr	Interv: 2hr		Interv: 2.5 hr	
All subjects											
Consent	X										
Coordinator visit	X	X				X		X	X	X	X
Masked clinical staff visit (for PFM measures)		X				X		X			X
Hx/PE (update)						X		X	X	X	X
Medication audit	X					X		X	X	X	X
UDE	X										
UDI (inclusion and primary outcome)	X								X	X	X
Other PRO questionnaires		X							X	X	X
Voiding diary	X*					X*	X	X*		X*	X*
PFM measures		X				X		X			X
Additional treatment**						X	X (both groups by phone)	X	X	X	X
Adverse events				X		X	X (both groups by phone)	X	X	X	X
Voiding function (PVR)	X					X					
Subjects randomized to intervention only											
BPTx visit			X			X	X	X		X	

Network

Protocol ESTEEM Statistical Analysis Plan

BPTx self-efficacy questionnaire		X								X	X
BPTx Adherence / Barrier questionnaire						X	X	X		X	X

5 ANALYSIS POPULATIONS

5.1 Intention-to-Treat (ITT) Population

The primary analysis population and the population for all secondary analyses will be the intention to treat population, which includes all randomized and eligible subjects. Subjects that are determined to be ineligible after randomization will be excluded from the analysis. For the analysis, all subjects will be assigned to the arm to which they were randomized irrespective of treatment received. The analysis will include randomized and eligible patients who provided outcome data at any follow up time point from 3 to 12 months.

It is possible that some women in both groups may cancel their surgical MUS procedure due to personal or other reasons. It is also possible that women randomized to BPTx may cancel their surgical procedure if they receive preoperative BPTx treatment and experience improvement. These women will still be included from an ITT perspective.

5.2 Per-Protocol (PP) Population

Per-protocol analyses (in which participants are analyzed according to the treatment actually received and their degree of compliance with those treatments) will be considered exploratory secondary analyses. The per-protocol population will be defined in the following way:

1. Participants randomized to the MUS only treatment arm are considered adherent to the protocol if they undergo MUS surgery.
2. Participants randomized to the MUS plus behavioral therapy treatment arm will be considered adherent to the protocol if all the following are true:
 - a. The participant undergoes MUS surgery.
 - b. The participant attends at least 4 out of 5 of the behavioral therapy sessions between 2-weeks and 6-months post-surgery
 - c. The participant reports performing exercises at least 4-5 times/week for weeks 2 and 6 or at least 2-3 times/week for week 8 at $\geq 75\%$ of attended visits between 2 and 8 weeks post-surgery, inclusive
 - d. The participant reports performing at least 30 contractions at $\geq 75\%$ of attended visits between 2 and 8 weeks post-surgery, inclusive
 - e. The participant reports no problems or, if participant reports problems with leakage, they also report using the "Knack" at $\geq 75\%$ percent of attended visits between 2 weeks and 6 months post-surgery, inclusive
 - f. The participant reports no problems or, if participant reports problems with urgency, they also report using the urgency suppression strategy at $\geq 75\%$ percent of attended visits between 2 weeks and 6 months post-surgery, inclusive
 - g. The participant reports no problems or, if participant reports problems with urgency or frequency, they also report using any other bladder training strategies at $\geq 75\%$ percent of attended visits between 2 weeks and 6 months post-surgery, inclusive

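### Three of the seven per-protocol criteria for the BPTx arm select on symptoms after randomization, with no matching filter for controls, so the exploratory PP contrast is prone to bias, probably towards BPTx

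*SAP*

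**What the plan says.** SAP 5.2 sets a different rule for each arm.

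- **Control arm:** "Participants randomized to the MUS only treatment arm are considered adherent to the protocol if they undergo MUS surgery". Nothing else is required.
- **BPTx arm:** a woman "will be considered adherent to the protocol if all the following are true", and seven items (a-g) follow.
  - Items a-d are surgery, attendance ("The participant attends at least 4 out of 5 of the behavioral therapy sessions between 2-weeks and 6-months post-surgery"), exercise frequency, and contractions ("The participant reports performing at least 30 contractions"). Items c and d must be met at 75% or more of the visits attended from 2 to 8 weeks. None of the four is waived for a woman without symptoms.
  - Items e-g each start with a waiver for women reporting no problems. Item e continues "The participant reports no problems or, if participant reports problems with leakage" and then requires use of the Knack. Item f says "if participant reports problems with urgency, they also report using the urgency suppression strategy". Item g applies the same pattern to urgency or frequency and other bladder-training strategies. All three use a 75% rule over visits attended from 2 weeks to 6 months.

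The SAP 4.6 schedule gives the adherence/barrier questionnaire to the intervention arm only. SAP 5.2 labels PP analyses as exploratory secondary. SAP 5.1 makes ITT the population for the primary and all secondary analyses, and SAP 9.1 says that every efficacy analysis uses ITT.

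**The concern.** The reports that decide e-g are made after randomization and concern leakage, urgency and frequency. The UDI measures closely related things: SAP 9.2 describes its questions C and D as leakage with urgency and leakage with activity, coughing or sneezing. The reporting window also spans the 3- and 6-month UDI assessments, which enter the longitudinal model in SAP 9.3.

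Items e-g can remove only symptomatic women. They thin out the women doing less well in the BPTx arm and leave the control arm whole. The filter cannot be mirrored in controls from the adherence questionnaire, because controls do not complete it. Use of the strategies is thus mixed with already doing well.

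At stake is how a PP result would be read. A favourable difference invites the message that BPTx works in women who adhere, and this definition cannot support that message.

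**Working it through.** **Figures in the plan.** The documents give no figure for the PP analysis. The size used below is the plan's 200 per arm (SAP 6.3). Inflating for 15% dropout gives 200/0.85 = 235.3, so 236 per arm and 472 in total, which matches the SAP. The SD of 50.4 is from SAP 6.1. The size of the bias does not depend on n; only the rejection rate does.

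**Assumed inputs (none is in the documents).**

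- p: share of women reporting problems
- u: share of those women failing e-g, after the 75% tolerance
- D: how much worse the 12-month UDI-total change is in women with problems
- f0, f1: share failing b-d among women without and with problems

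**Model, with no true effect.** In the BPTx arm the retained shares are r0 = (1-p)(1-f0) without problems and r1 = p(1-f1)(1-u) with problems. All controls are kept.

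Bias favouring BPTx = D × [p - r1/(r0 + r1)]

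SE = 50.4 × √(1/200 + 1/(200(r0 + r1))), with two-sided alpha 0.05.

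**Items e-g alone (f0 = f1 = 0).**

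| D | p | u | r1/(r0+r1) | Bias (points) | Two-sided rejection |
|---|---|---|---|---|---|
| 10 | 0.3 | 0.2 | 0.24/0.94 = 0.2553 | 10 × 0.0447 = 0.4 | 5.1% |
| 20 | 0.5 | 0.3 | 0.35/0.85 = 0.4118 | 20 × 0.0882 = 1.8 | 6.3% |
| 35 | 0.6 | 0.5 | 0.30/0.70 = 0.4286 | 35 × 0.1714 = 6.0 | 19.1% |

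In the middle row SE = 50.4 × √(1/200 + 1/170) = 5.26. Simulation with 20,000 replicates gave 6.6% for the middle row and 18.9% for the last. A failure rate in b-d that is the same with and without problems cancels out of the bias.

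**Larger assumed gap.** Take a latent correlation of 0.5 between early problems and UDI change, with 40% of women problem-free. The gap is 0.5 × 50.4 × 0.3863/(0.4 × 0.6) = 40.6 points. With p = 0.6:

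- u = 0.2: 40.6 × (0.6 - 0.48/0.88) = 2.2
- u = 0.4: 40.6 × (0.6 - 0.36/0.76) = 5.1
- u = 0.6: 40.6 × (0.6 - 0.24/0.64) = 9.1

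**When b-d depend on symptoms.** The same three pairs of p and u are used, with D from 10 to 35.

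- Symptomatic women lapse more (f0 = 10%, f1 = 30%): 0.9 to 8.1 points, rejection 5.3% to 27.8%.
- Problem-free women lapse more (f0 = 50%, f1 = 20%): -1.9 to +1.9 points. The low end is 35 × (0.3 - 0.192/0.542) = -1.9.
- Bias is zero when f0 = 1 - (1-f1)(1-u). With f1 = 20% and u = 30%, that is 1 - 0.8 × 0.7 = 44%.

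**With e-g dropped (u = 0) and b-d unrelated to symptoms.** Bias is 0 and the rejection rate is 5.0%.

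**Week 4.** Protocol 5.4 places post-operative sessions at 2, 4, 6 and 8 weeks and 6 months. Item 2c reads "The participant reports performing exercises at least 4-5 times/week for weeks 2 and 6 or at least 2-3 times/week for week 8". The 75% rule covers all attended visits from 2 to 8 weeks, yet week 4 has no stated threshold, so two programmers could build different PP sets.

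**The case against.** A reader might infer that a problem-free BPTx woman is per-protocol automatically. The text does not say that. She must still have surgery, attend, exercise and report the contractions; only three of the seven criteria are waived.

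A reader might also infer that the PP analysis must favour BPTx. That is likely but not assured. Women who feel well may stop attending or exercising, and then b-d remove them and can cancel or reverse the bias. The model further assumes that symptomatic women removed by e-g have the same outcomes as those retained. If non-users have milder problems, removing them works against BPTx. The documents have no data on either point.

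The 75% tolerance also softens the rule. With 4 or 5 sessions attended, one visit with problems and no strategy use still passes (3/4 or 4/5). A single fixed problem status per woman represents this only roughly.

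The waiver has a clinical logic, since a woman without urgency has no occasion to suppress it. And the plan limits the consequence: PP is exploratory, ITT governs the primary and secondary conclusions, and the display list in SAP 15 names no PP table.

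All of this stands, and it limits the size, certainty and reach of the point. It does not alter the structure: e-g filter on symptoms after randomization, in one arm, and can remove only symptomatic women.

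**Conclusion.** The point holds for the exploratory PP analysis. As written, PP membership in the BPTx arm is partly decided by symptoms close to the outcome, and controls face no counterpart. With the other criteria neutral and no true effect, this favours BPTx by about 0.4 to 6 UDI points for assumed gaps of 10 to 35 points. It reaches about 9 only with a gap near 41 points and 40% strategy use among symptomatic women. Only the SD and the sample size come from the documents; p, u, D, f0 and f1 are assumptions. The direction is probable rather than certain.

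It would be wrong to infer that the trial's main result is compromised, because SAP 5.1 and 9.1 keep it on ITT. The missing week-4 threshold is a wording gap and adds nothing to the argument about direction.

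**What to change.** 1. Define BPTx adherence in SAP 5.2 by the criteria that do not refer to symptoms (2a-2d), and report strategy use (2e-2g) descriptively.
2. Label the PP contrast as a non-randomized comparison wherever it is reported.
3. Add, as a supplementary analysis, a complier-average causal effect with randomization as the instrument and compliance based on session attendance. State the exclusion restriction: assignment affects outcome only through compliance as defined. Women who attend some sessions but fall short of the cut-off still receive therapy, so a binary definition could overstate the effect. Include a sensitivity analysis for partial attendance.
4. State in 2c how the week-4 visit is judged.
5. Reconcile SAP 5.2 with SAP 9.1 on whether PP efficacy analyses are run at all.

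The cost is SAP wording and minor programming, with no new data. The BPTx PP set changes size and no longer reflects strategy use. Items b-d still filter one arm after randomization, so the change reduces selection without removing it.

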6 SAMPLE SIZE DETERMINATION

This study is designed to compare the relative effectiveness of MUS and MUS combined with BPTx. Power and sample size calculations were generated to determine the sample size needed to test for treatment difference favoring MUS combined with BPTx across the study arms for a variety of assumptions about effective size and follow-up time. Sample size estimates are based on simulations using analysis methods accounting for both the rate of additional treatment in the two groups as well as UDI total score or subscore values over the 12 month follow up. We assumed that 30% of women in the MUS only group and 20% of women in the MUS+BPTx group would request additional treatment. In TOMUS, 10-12% of women who had baseline MUI had persistent UUI postoperatively based on MESA responses and/or initiation of anticholinergic treatment.²⁴ In Barber's TVT vs TOT equivalence trial, 70% reported baseline MUI and postoperatively, 30% of all women reported bothersome UUI with 16% of subjects on anticholinergic treatment postoperatively.³¹ In Abdel-Fattah's transobturator MUS trial, 25% reported worsening OAB and almost all of these women were on anticholinergic treatment postoperatively.³⁴ In Palva's TVT vs TVT-O trial, 174 women reported preoperative UUI and of these, 7 women (4%) had tried anticholinergics postoperatively after 3 years. Therefore, based on existing MUS trials, the rate of additional treatment for OAB ranges from 4-25%, supporting our conservative assumption that 30% of women will request additional treatment in the MUS only group.

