6.1 Primary Outcome

The MID for the UDI-total score published by Dyer et al. is estimated to be 35 points.⁵⁰ Assuming a two-sided alpha of .05, SD of 50.4, and true difference in mean change from baseline in UDI-total scores at 1 year between treatment groups of 35, 75 women per group would provide 90% power to detect a statistically significant difference between groups.

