6.3 Final Sample Size

Using 200 per group as our base estimate and adjusting for 15% dropout post-operatively results in a total sample size of 472 randomized to treatment. Additionally, this sample size will provide approximately 90% power to detect a difference as small as 19 between treatment groups for the UDI-total score, and a difference as small as 16.5 points with 80% power.

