7.7 Multiple Comparisons and Multiplicity

The primary hypothesis and two secondary hypotheses will be tested at a nominal two-sided type I error of 0.05. All p-values for any baseline and demographic characteristics, secondary outcomes, and safety parameters will be for descriptive purposes only.

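### The per-protocol rule in SAP 5.2 drops symptomatic non-users from the BPTx arm only, so the exploratory per-protocol contrast is open to symptom selection, probably favouring BPTx

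*SAP*

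**What the plan says.** SAP 5.2 sets different tests for the two arms.

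- **Control arm:** "Participants randomized to the MUS only treatment arm are considered adherent to the protocol if they undergo MUS surgery". Nothing else is asked.
- **BPTx arm:** all of 2a-2g must hold. 2a is surgery, 2b is at least 4 of 5 postoperative sessions, 2c is exercise frequency and 2d is number of contractions. 2e-2g concern the leakage, urgency and bladder-training strategies. Each can be met in two ways. For urgency (2f): "The participant reports no problems or, if participant reports problems with urgency, they also report using the urgency suppression strategy at" 75% or more of attended visits between 2 weeks and 6 months.

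The Adherence / Barrier questionnaire is scheduled for the intervention arm only (Protocol Table 11, SAP 4.6).

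The same section calls per-protocol analyses exploratory secondary. SAP 9.1 runs all efficacy analyses on the ITT population. SAP 7.7 assigns error rates elsewhere: "The primary hypothesis and two secondary hypotheses will be tested at a nominal two-sided type I error of 0.05". No per-protocol endpoint, model or alpha is named, and SAP 15 lists no per-protocol display.

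**The concern.** Leakage, urgency and frequency are what the UDI scores. Conditions 2e-2g are judged on those symptoms after randomisation, in a window that runs to the 6-month visit, where the UDI is also taken. A BPTx woman with problems who uses the strategies stays. One with problems who does not use them goes. One without problems passes 2e-2g whatever she does, although she must still meet 2a-2d. Every operated control stays, including the symptomatic ones.

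If early symptoms predict the 1-year UDI, the retained BPTx women have better outcomes than the arm they came from, even when BPTx does nothing. A non-zero correlation is plausible: SAP 9.1 itself allows missing 12-month UDI to depend on 3- and 6-month outcomes.

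At stake is how the result is read. SAP 5.2 presents the analysis as one by treatment received and degree of compliance. Beside a null ITT result, a per-protocol difference could be taken to mean that the programme works when followed.

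**Working it through.** **Inputs from the documents.** Two-sided alpha 0.05 (SAP 7.7). SD of UDI-total change 50.4: "Assuming a two-sided alpha of .05, SD of 50.4, and true difference in mean change from baseline in UDI-total scores" of 35 (SAP 6.1). 1:1 allocation (SAP 4.3). 200 evaluable women per arm (SAP 6.3). Five postoperative visits and the 75% rule (SAP 5.2). True effect set to 0, the null in Protocol 1.1.

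**Inputs the documents do not give, taken as ranges.** Share with problems at a visit: 30-50%; one cited trial reports 30% bothersome UUI after a sling. Strategy use when there is a problem: 50-90%. Correlation of early symptoms with 1-year UDI change: 0-0.5. Women passing the other BPTx conditions: 70%.

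**The plan's own figure.** 200 / 0.85 = 235.3, rounded up to 236; 2 x 236 = 472, as stated. For UDI-total the plan says "75 women per group would provide 90% power to detect a statistically significant difference between groups". The plain two-means formula gives 2 x (1.96 + 1.282)^2 x (50.4/35)^2 = 43.6, or 44 per group. The plan says "Sample size estimates are based on simulations using analysis methods accounting for both the rate of additional treatment in the two groups" and does not give the settings, so this gap is not shown to be an error, and the point does not depend on it.

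**Step 1, formula.** Suppose 2e-2g remove a share x of BPTx women whose change is D points worse than that of the women kept. Under a zero effect:

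- bias = x * D
- SE = 50.4 * sqrt(1/n_PP + 1/200), with n_PP = 200(1 - x)
- rejection = Phi(bias/SE - 1.96) + Phi(-bias/SE - 1.96)

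| x | D | bias | SE | rejection |
|---|---|---|---|---|
| 0.1 | 10 | 1.0 | 5.18 | 5.4% |
| 0.2 | 25 | 5.0 | 5.35 | 15.5% |
| 0.3 | 25 | 7.5 | 5.55 | 27% |
| 0.4 | 40 | 16.0 | 5.82 | 79% |

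**Step 2, simulation of the symptom conditions.** Zero effect, 200 per arm, two symptom domains, strategy use unrelated to severity, two-sided t-test of retained BPTx women against all controls, at least 2,000 replicates per cell. Cells show rejection and, in brackets, bias in UDI points; negative favours BPTx.

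| Problems | Use | corr. 0 | corr. 0.3 | corr. 0.5 |
|---|---|---|---|---|
| 30% | 50% | 5.7% (-0.2) | 20.6% (-7.3) | 46.8% (-12.2) |
| 30% | 70% | 4.6% (0.2) | 10.5% (-4.4) | 23.2% (-7.3) |
| 30% | 90% | 4.6% (0.1) | 5.4% (-1.2) | 6.2% (-2.0) |
| 50% | 50% | 4.8% (0.0) | 29.3% (-10.4) | 66.2% (-18.0) |
| 50% | 70% | 5.4% (0.0) | 16.4% (-6.3) | 36.8% (-10.9) |
| 50% | 90% | 5.0% (0.0) | 6.3% (-1.8) | 7.6% (-2.6) |

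The ITT test in the same runs rejected 4.0-5.6% of the time.

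**Step 3, formula against simulation.** In the 30% / 70% / 0.5 cell, 51% of the arm is kept, so n_PP = 102 and SE = 50.4 * sqrt(1/102 + 1/200) = 6.13. A bias of 7.3 gives 7.3/6.13 = 1.19 and rejection of about 22%, against 23.2% simulated.

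**Step 4, all three symptom conditions.** With three symptom items, correlation 0.3-0.5 and 30-50% with problems, rejection is about 11-79% at 50-70% use and 6-9% at 85% use. It is about 5% at zero correlation.

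**Step 5, changing the assumptions.**

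- Use that rises with severity cuts rejection from 42% to 11% in one cell.
- If symptomatic women comply better with 2b-2d (correlation 0.3), 23.2% falls to 9.6%. At 90% use the bias becomes 1.6 points against BPTx (5.8%).
- With adherence resting only on conditions unrelated to symptoms, as 2a-2d were modelled, rejection is 5.4% and bias 0.2.
- If only the no-problems wording is struck and women without problems do not use strategies (50% with problems, 90% use, correlation 0.5), the bias is 27.8 points against BPTx and rejection is 66%.

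**The case against.** The case against is substantial, and three stronger readings fail.

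A reader might infer that the rule biases the result toward BPTx by construction. It does not. The size depends on problem prevalence, strategy use and correlation with the 1-year UDI, none of which the documents give. High strategy use nearly removes the inflation, use that rises with severity shrinks it, and better attendance by symptomatic women can slightly reverse it.

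A reader might infer that the trial's conclusions are at risk. They are not: the analysis is exploratory, and the primary and secondary analyses are ITT. The t-test above is a stand-in, because the SAP specifies no per-protocol test; it does not reproduce the mixed model or the additional-treatment rule of SAP 9.3.

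A reader might blame the no-problems branch. That branch is a reasonable not-applicable clause, since urge suppression needs urgency. The selection comes from removing symptomatic non-users.

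It can also be said that without 2e-2g adherence ignores three of the four BPTx components (Protocol 5.4), and that a complier-average estimate makes a doubtful assumption about partly treated women. Both points stand as limits to state. Neither removes the asymmetry: one arm is filtered on early values of the outcome's own symptoms and the other is not.

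**Conclusion.** The concern holds as a defect of an exploratory analysis. The per-protocol contrast in SAP 5.2 is open to symptom selection, probably in favour of BPTx, and can reject under a zero effect. The 11-79% range is conditional on the assumed 30-50% with problems, correlation 0.3-0.5, 50-70% strategy use and use unrelated to severity; it is not a prediction for this trial. At the unfavourable end the bias (18.0 points in the table) exceeds the 16.5 points that SAP 6.3 says the trial can detect with 80% power, so an artefact could look like a treatment effect. A correction is worth making because it is cheap and the misreading is easy.

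**What to change.** 1. Delete 2e, 2f and 2g entirely from the per-protocol definition, so that adherence rests on 2a-2d, whose wording does not refer to symptoms. Do not merely strike the no-problems words: that would penalise symptom-free women and can reverse the bias.
2. Report strategy use descriptively in the BPTx arm.
3. Beside the per-protocol result, report a complier-average estimate on the ITT sample with randomised assignment as the instrument, adjusted for site and urge-IE group and labelled exploratory. Say how it treats UDI scores after additional treatment, which SAP 9.3 sets to missing.

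**Cost.** SAP wording and one extra model, with no new data.

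**Limits to state.** The instrumental estimate has a wider interval. It assumes no BPTx benefit in women below the adherence threshold, which is doubtful for those who attended some sessions. Adherence selection may remain through 2b-2d. SAP 13 reports in the past tense that Kaplan-Meier methods replaced the planned survival model, so some outcome data appear to have been analysed already; if so, label the revised definition and the added estimate post hoc.
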